- For both intervention areas and selected comparison areas (e.g. the closest matched comparison area per intervention area), early years services data will generate an understanding about systems change within early years provision and help us determine whether any changes detected over time are due to ABS or occur for another reason;
- Administrative data on child and family outcomes in the five ABS areas against those in other similar matched areas, will provide estimates of the impact of the programmes across the whole of the eligible population, to test whether the work of the five areas has area-wide impacts;
- Data on costs and services from the five areas will be combined with our findings on the impact of the programme, which will permit us to measure the cost-effectiveness of the programme, both overall and for each site.

The data collection within intervention and comparison areas comprises two components:

1. Cross-sectional, baseline surveys of parents of 1, 2 and 3 year-olds in the first year of the programme (2016/17), which will provide baseline data on outcomes for current parents and children in all our areas prior to the implementation of A Better Start. Baseline surveys will be conducted in both intervention and matched comparison areas, allowing us to (a) check that the intervention and comparison areas are the same prior to the start of the programme; and (b) to allow us to measure changes in outcomes over time in both the intervention and comparison areas.
2. A large cohort study, starting recruitment in 2019, which will generate data on impact. Families will be tracked until the children are 5-years of age. In addition to parent and teacher-report data, we will collect additional data for a sub-sample of families, using measures that will provide valuable information, but which are too costly to collect and/or process across the entire sample.

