### 5.5.3 Sample Size Justification

The sample size for the cohort study has been set with the primary aim, after attrition, of generating 815 interviews with parents of three year olds in programme areas and 555 in comparison areas. The 'headline' estimates of impact will be based on difference-in-differences estimates. That is, change since baseline for children of the same age group in ABS areas, minus change since baseline in comparison areas. For outcomes at age 1, for instance, this will be based on the four sets of data within the second row of the table (i.e. 500; 270; 1200; 825). Samples of this size will enable detection of effect sizes of 0.25 standard deviations (with 80% power). For binary outcomes, this equates to being able to detect an impact of around 12 percentage points (i.e. if 12% of children in ABS areas have a better outcome at age 1 as a direct result of the programme, a difference-in-difference estimate should be observed that is significantly different to zero). At Age 2 the cohort sample sizes will have been subject to attrition, and the detectable effect size at age 2 will be just over 0.25; and with further attrition at Age 3, the detectable effect size will be 0.26.

In practice, it is hoped that no real differences in the baseline outcomes for ABS and comparison areas will be observed. If baseline differences can be ruled out, then the evaluation can focus on comparing the ABS and comparison cohort samples. This will greatly improve the statistical power. For example, at age 1, if only the two cohort samples of 1200 and 825 were compared, effect sizes of 0.13 standard deviations could be detected.

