## 6.2 Data Analysis

The baseline and cohort studies are complex and cover a very large range of outcomes, over multiple data collection points. The longitudinal cohorts will generate a steady stream of rich and complex data the analysis of which is to be planned in detail before each analysis stage. A balance will need to be struck between exploring the data in depth, so that the data contribute as much as possible to our understanding of the nature and size of programme effects, and contributes to the evaluation in a formative way, but without any risk of 'fishing' for positive results. We plan to manage this as follows:

At the start of each analysis phase, and before any data analysis has started, the team will generate a detailed analysis plan. This will cover:

1. The outcomes to be included in the analysis, including how they are to be coded;
2. The datasets to compare (e.g. whether the analysis will compare newly created datasets with earlier ones from the evaluation (including the baseline), or whether the comparison will be cross-sectional programme v comparison);
3. Whether there are to be any sub-groups analyses;
4. How 'explanatory' variables are to be used;
5. How the analysis will be done (such as when, and how, propensity score matching will be used, regression analysis, and so on);
6. How to present the results (i.e. tables, graphs etc.)

The decisions on the analysis plan each time will partly be driven by programme theory (that is, what changes might we expect to observe, given the logic of the programme). But there will also be new hypotheses to be tested, these being generated by other strands of the evaluation (such as any suggestions from the implementation study that the programme is looking to be particularly successful for some groups of parents and less so for others).

Over and above this planned analysis, we will include some exploratory analysis at each phase – such as running impact estimates for a range of sub-groups over and above the sub-groups for which theory suggests that differences should arise. This analysis will be kept separate from the main analysis, and reported on as separate. The intention is to use the data to identify any potential anomalies in impacts that can then be fed back into the implementation study for testing.

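### Section 5.5.3 lets the headline comparison move from difference-in-differences to cohort-only if baseline differences are ruled out, which the baseline samples are too small to show

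*Protocol*

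**What the plan says.** Section 5.5.3 names the main estimator: "The 'headline' estimates of impact will be based on difference-in-differences estimates". At age 1 it uses baseline samples of 500 and 270 with cohort samples of 1200 and 825, and gives a detectable effect of 0.25 SD at 80% power. The next paragraph opens a second route. It states that "it is hoped that no real differences in the baseline outcomes for ABS and comparison areas will be observed", and then: "If baseline differences can be ruled out, then the evaluation can focus on comparing the ABS and comparison cohort samples". The gain is put as "if only the two cohort samples of 1200 and 825 were compared, effect sizes of 0.13 standard deviations could be detected".

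Section 5.1 gives, as one of two purposes of the baseline survey, to "check that the intervention and comparison areas are the same prior to the start of the programme"; the other is to measure change over time. Section 6.2 has a detailed plan written before each analysis phase. Its item 2 covers which datasets to compare, with earlier ones including the baseline, "or whether the comparison will be cross-sectional programme v comparison". Section 6.2 also says that standard errors will allow for matching, non-response weights and between-comparison-area effects. It mentions no allowance for choosing the estimator from the data.

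**The concern.** The programme areas were competitively selected for need, not randomised. DiD protects against fixed differences in outcome between programme and comparison areas. The sentence in section 5.5.3 would let that protection be set aside on the strength of the baseline result. If the baseline is too imprecise to show a gap that matters, a pre-existing gap can pass the check and then be read as programme effect. The promised gain in detectable effect, from 0.25 to 0.13 SD, would then be bought with bias and a raised false-positive rate in the main conclusion.

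**Working it through.** **Inputs.** Baseline sizes, programme/comparison (section 5.5.1): 378/225, 313/361 and 208/216 at ages 1, 2 and 3. Section 5.5.3 uses 500/270 instead, so both are run. Cohort sizes (Table 2): 1200/825, 1060/720 and 815/555. Outcome SD = 1, two-sided 5% (assumed; it reproduces the stated figures), no design effect.

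**The plan's own figures.** Detectable effect = (1.96 + 0.8416) × √Σ(1/n).
- DiD, age 1: 2.8016 × √(1/500 + 1/270 + 1/1200 + 1/825) = 2.8016 × 0.0880 = 0.247 (stated 0.25).
- DiD with 500/270 at ages 2 and 3: 0.251 and 0.262 (stated just over 0.25, and 0.26).
- Cohort-only, age 1: 2.8016 × √(1/1200 + 1/825) = 2.8016 × 0.0452 = 0.127 (stated 0.13).

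All reproduce.

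**Precision of the baseline check.** Half-width = 1.96 × √(1/n₁ + 1/n₀). For age 1: 1.96 × √(1/378 + 1/225) = 1.96 × 0.0842 = 0.165.

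| Baseline | SE | 95% half-width | Power to see a 0.13 SD gap | Cohort-only detectable effect |
|---|---|---|---|---|
| Age 1, 378/225 | 0.0842 | 0.165 | 34% | 0.127 |
| Age 2, 313/361 | 0.0772 | 0.151 | 39% | 0.135 |
| Age 3, 208/216 | 0.0971 | 0.190 | 27% | 0.154 |
| Age 1, 500/270 | 0.0755 | 0.148 | 41% | 0.127 |

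In every row the half-width exceeds the effect that the cohort-only comparison could detect. This does not depend on any reading of the rule. Clustering by area would widen the intervals: with an assumed design effect of 1.3, the age 1 half-width (378/225) is 0.188.

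**Reading A: equivalence within 0.13 SD** (two one-sided 5% tests). The switch needs |observed difference| + 1.645 × SE < 0.13. The term 1.645 × SE is 0.138, 0.127 and 0.160 at ages 1, 2 and 3, and 0.124 with 500/270. With truly identical areas the switch therefore occurs in 0%, 3% and 0% of cases, and about 6% with 500/270. Type I error stays at about 5-6%. For 80% power to show equivalence when the true difference is zero, the margin would have to be about 0.25, 0.23 and 0.28 SD (0.22 with 500/270).

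**Reading B: baseline difference not significant at two-sided 5%.** Simulation with 2,000,000 draws per case, true programme effect zero, and the same true gap *d* at baseline and in the cohort (parallel trends). Baseline estimate b ~ N(d, SE_b²), cohort estimate c ~ N(d, SE_c²). If |b|/SE_b < 1.96, test c; otherwise test c − b. Section 5.5.1 baseline sizes, ages 1 / 2 / 3:

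| True gap d | Switch occurs | Type I error | Bias (SD) |
|---|---|---|---|
| 0 | 95 / 95 / 95% | 7.6 / 7.3 / 7.5% | 0 |
| 0.05 | 91 / 90 / 92% | 21 / 19 / 16% | 0.034 / 0.033 / 0.034 |
| 0.10 | 78 / 75 / 82% | 49 / 43 / 39% | 0.053 / 0.050 / 0.058 |

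With 500/270 at age 1, type I error is 7.4%, 20% and 47% for the three gaps. DiD kept throughout gives 5.0% in every case.

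**In between: equivalence margin 0.20 SD.** With a 0.10 SD gap, type I error is 22%, 22% and 13% at ages 1, 2 and 3.

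**The case against.** The strongest reply is that the protocol states no switching rule that could be simulated. It names no test, and to rule out a difference, taken literally, is to exclude it. On that reading type I error hardly moves. This stands, and it means that the 39-49% figures are not the plan's error rate. They follow from one assumed rule and an assumed residual gap that no document supplies. The non-significance reading is still plausible, because the preceding sentence speaks of no real differences being observed.

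A reader might infer that the plan abandons DiD. It does not: the wording is permissive, DiD remains the headline and the basis of the stated powering, and section 6.2 describes the age 3 analysis as a comparison of change since baseline.

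A reader might also infer that section 6.2 item 2 repeats the switch. It does not: it lists what each phase's plan will specify, nothing ties it to the baseline result, and a cross-sectional option is needed for antenatal, 4-month and age 5 outcomes, which have no baseline survey.

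Other safeguards exist. Comparison areas were chosen by distance on seven relevant indicators, and groups are to be propensity-matched. Both may shrink the residual gap, but neither corrects for picking the estimator after seeing the baseline.

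Finally, DiD holds 5% only under parallel trends, and the planned baseline frame (a commercial list) differs from the cohort frame (maternity booking). That limits DiD as a perfect benchmark; it is no argument for dropping the baseline.

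**Conclusion.** The point holds in a bounded form. The baseline samples cannot rule out a pre-existing difference as large as the effect that the cohort-only comparison is meant to detect; this rests only on the stated sample sizes and a 95% interval. What follows depends on how the undefined condition is read. A strict margin makes the switch, and so the 0.13 SD figure, practically unattainable. A lenient test lets it happen often and raises type I error. The size of that rise is conditional on the assumed 5% pre-test, parallel trends, no clustering and the residual gap after matching. With no gap there is modest inflation and no bias, so a general statement that the pre-test biases the estimate would go too far. With a gap of 0.10 SD the bias is about 0.05 SD. This should be fixed, because it concerns the choice of the headline estimator.

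**What to change.** - **Section 5.5.3:** delete the sentence that allows the switch. State that DiD is the headline estimator for every outcome measured at baseline (ages 1, 2 and 3), whatever the baseline result. Do not present 0.13 SD as achievable for the headline estimate.
- **Reporting:** give the cohort-only contrast as a labelled sensitivity analysis, with the baseline difference and its confidence interval beside it.
- **Section 6.2 item 2:** keep the cross-sectional comparison as the main analysis only for outcomes with no baseline survey (antenatal, 4 months, age 5).
- **Sections 5.5.1 and 5.5.3:** while editing, reconcile the baseline sizes (378/225 against 500/270 at age 1), since the detectable effects depend on them.

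The cost is wording and a more modest power claim. The detectable effect stays at the DiD value: about 0.25-0.26 SD as stated, or 0.27, 0.26 and 0.31 SD at ages 1, 2 and 3 with the section 5.5.1 baseline sizes. No new data are needed.

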### 5.5.4 Recruitment Pilot Sample

A total of 300 interviews are planned, with 150 interviews starting at 28-weeks antenatal, running until 4-months postnatal across all five programme intervention areas, and 150 across five of the fifteen comparison areas. The five pilot comparison areas are: **Stoke-on-Trent; Derby; Hammersmith and Fulham; Birmingham**, and; **East Kent** (matched target wards within each area are listed on page 13).

Sample sizes for the pilot study are sufficient to test whether the recruitment process is working as planned. There will be no formal statistical analysis of the difference in survey outcomes between these two pilot samples so a power calculation is not appropriate here. (In fact, the evaluation does not expect to observe any large statistical differences between the two groups because the mothers will be recruited before any major impacts of ABS are expected).

### 5.5.5 Sub-sample Sizes

The evaluation has been costed to collect the main outcomes on the whole sample. However, a number of objective measures have been built in, which are more costly to administer and process; therefore these have been built into the study using a sub-sample design, with large enough power but minimising cost. The sub-sample sizes are listed in Table 3. Each of the subsample outcomes has been powered to detect change in the region of 0.25 standard deviations.

**Table 3. Sub-sample Sizes (I = Intervention Area and C = Comparison Area)**

	Hair		Buccal		CARE Index		Story Stem	
	I	C	I	C	I	C	I	C
Birth	100	100	100	100	-	-	-	-
Age 1	-	-	-	-	300	105		
Age 2	100	100	100	100	-	-	-	-
Age 3	-	-	-	-	-	-	375	375

## 5.6 Comparison Areas Selection

The evaluation will select and recruit three matched comparison areas per ABS intervention area. Given that not all the potential comparison sites approached will agree to take part, a total of ten comparison areas per ABS area have been identified, with three 'preferred' areas and a reserve list of seven others.

The National Foundation for Educational Research (NFER) 'Children's Services Statistical Neighbour Benchmarking Tool' was used to do this. This tool was designed so that Local Authorities (LAs) could compare themselves with other 'similar' LAs on their progress on Every Child Matters (ECM) outcomes.

The evaluation design has set out to achieve a set of comparison areas per ABS LA that are currently very similar to the ABS area in terms of any indicators that are:

- a) Publically available; and
- b) Are likely to be highly correlated with the outcomes being measured in the evaluation surveys

Led by statistical expertise, the evaluation team agreed that the most relevant indicators to use were:

- Percentage of babies of low birth weight;
- Prevalence of maternal smoking;
- Prevalence of breast feeding;
- Percentage obesity at age 5;
- Percentage with good level of development at EYFS;
- Percentage of pupils achieving 5+ GCSEs;
- Percentage of children in care.

The NFER model provides ten statistical neighbours per LA. So, for instance, Blackpool's ten are:

- Torbay
- Tameside
- Redcar & Cleveland
- Plymouth
- Hartlepool
- North East Lincolnshire
- Barnsley
- Isle of Wight
- Doncaster
- Stoke-on-Trent

The variables used by NFER to generate the neighbours include a combination of relative deprivation, economic profile, urban/rural, and ethnicity.

The ten LAs that NFER identify are in priority order. For example, the closest match to Blackpool is Torbay. This means that in principle the evaluation could simply use the first three NFER LAs per ABS LA as its comparison areas. However, we plan to make use of all ten and reprioritise them so that they are more closely aligned with ABS outcomes.

In order to identify which of the ten NFER areas are the best matches to the ABS area across these seven indicators, an overall 'distance score' was created between the ABS and each of the potential comparison areas (with the distance score being based on a Euclidean distance metric, and using standardised scores per indicator). The three areas at shortest distance to the ABS area are the three that have been selected in the first instance, and the matching of programme wards with comparison wards is currently ongoing.

We will also aim to establish in all areas prioritised as comparison sites, whether there is any evidence of early years' initiatives that might make it unsuitable as a comparison area for ABS.

## 5.7 Data Collection Instruments

### 5.7.1 Evaluation Outcome Measures

The impact and economic evaluation will assess short- (birth – 3 years) and medium- (4-5 years) outcomes in each of three key outcome domains (e.g. social and emotional development; speech and language; nutrition). It will also measure parental outcomes that are strong predictors of infant/child functioning. This will be undertaken using a range of bespoke and universal (i.e. standardised and validated) instruments.

The outcomes framework involves the collection of the following types of data:

- **Demographics and other matching data**
- **Individual trajectories (short-, medium- and long-term)**
  - Parental outcomes
  - Child outcomes
- **Service-use:** detailed data that will enable understanding of how any programme impacts have been achieved, and that will inform the economic evaluation
- **Population level data:** gathered using sources such as Chimat or LAIT for each to complement the data on the families receiving the intervention and that will assess area-level impact.

Parental outcomes will include measures of: health and mental health; relationships with the child; parental functioning; and parental context (e.g. social support).

Child outcomes will include measures of: nutrition and health; socio-emotional development; and language, cognitive and school outcomes.

Additional sub-sample data will be collected using a number of measures (e.g. buccal swabs to assess epigenetic changes, video-taped coding of parent-child interaction, story-stem exercise to measure attachment, and observations of the home learning environment).

### 5.7.2 Primary Outcome Measures

Since this is a long-term formative evaluation, a number of key primary outcome measures have been carefully selected for parents and children within each of the domains of socio-emotional, nutrition, and language and cognitive development.

The key outcomes being measured are as follows:

#### *Nutrition*

- a) Method of feeding will be assessed in pregnancy and the first year using bespoke questions.
- b) Weight/length/height will be assessed using standard data at birth and following school entry; and using routine techniques (i.e. scales) at all time-points.
- c) Patterns of food intake will be assessed using the Children's dietary questionnaire (CDQ) at 3 and 5 years.
- d) Feeding practices will be assessed using the Comprehensive Feeding practices Questionnaire (CFPQ) at 3 and 5 years.

#### *Socio-Emotional Functioning*

- a) At 12 months, socio-emotional functioning will be assessed using the **Brief Infant Toddler Social Emotional Assessment Scale (BITSEA)**.
- b) Mother-infant interaction will be assessed in a sub-sample of children using the **CARE Index** coding of videotaped interaction.
- c) An objective measure of stress will also be undertaken by measuring cortisol levels in a subsample only using small hair samples from mother at birth and the child at 2 years;

- d) At 2, 3 and 5 years, social competence will be assessed using the **Adaptive Social Behaviour Inventory (ASBI)**.
- e) At 5 years, behavioural development will be assessed using the **Strengths and Difficulties Questionnaire (SDQ)**. At ages 5-7, parents and teachers will complete the ASBI and SDQ.
- f) Self-Esteem will be assessed using a brief child-report instrument - the **Piers-Harris Self-Concept Scale**.
- g) Attachment will be assessed in a subsample only at 3 years using the **Story Stem Attachment Dolls House**.

### *Speech, Language and Learning*

- a) At 12 months, motor, language and cognitive development will be assessed in a sub-sample of children using the Bayley Scales (BSID-II MDI)
- b) At 2 years, vocabulary knowledge will be assessed using the parental-report Sure Start Language Measure (SSLM) across the whole sample
- c) At 3 years, expressive vocabulary and comprehension (understanding of spoken language) will be assessed using the BAS III
- d) At age 5, the Early Years Foundation Stage Profile (EYFSP) will provide a teacher assessment of children's development and readiness for school in a range of areas (physical, personal social and emotional, communication and language, literacy, maths, understanding of the world expressive arts and design)
- e) At age 6, a measure of children's phonics decoding skills will be provided by the Year 1 phonics test

### 5.7.3 Key Validated Measures

#### EQ-5D-5L

---

Overall health and parental psychological functioning will be measured at 26-36 weeks' antenatal, 4-months postnatal, and again at ages-1, 2 and 3, in part through the use of the EQ-5D-5L – a standardised instrument providing a measure of health outcome. Applicable to a wide range of health conditions, the EQ-5D-5L questionnaire provides a simple descriptive profile and a single index value for health status. It is cognitively simple, taking only a few minutes to complete. Instructions to respondents are included in the questionnaire.

#### State-Trait Anxiety Inventory

---

Parental psychological functioning will also be assessed using the 6-item State-Trait Anxiety Inventory (STAI), an instrument that quantifies adult anxiety. The STAI is used to simplify the separation between state anxiety and trait anxiety, feelings of anxiety and depression, and the short version uses a 6-question response, which is very quick and simple for the respondent to complete. The questionnaire is split into the S-Anxiety T-Anxiety scales. The questions are answered on the basis of a 1-4 scale, with the focused areas including worry, tension, apprehension and nervousness. Respondents will be asked to complete the 6-item STAI as part of the 26-36 weeks' antenatal and 4-months postnatal, questionnaires.

